5.8 Treatment Compliance

Treatment compliance will be assessed by the Investigator based on Subject Diary Card completion at each study visit following the Baseline. Compliant subjects are defined as those who have completed at least 75% and no more than 125% of study drug applications until treatment success or for a maximum of four cycles of treatment.

5.9 Accountability, Destruction and Return of Study Supplies

The Sponsor will supply sufficient quantities of the study drug for the following:

- 1. Completion of this study
- 2. Samples retention, as per applicable regulations described in Section 5.4.

The study pharmacist or designated study personnel will maintain a Study Drug Accountability Log itemizing all study drug received, dispensed to and returned from each subject during the study. All

Confidential Page 32 of 59

dispensed tubes must be accounted for, and any discrepancies explained. Study site should contact site Clinical Research Associate (CRA) in the case if any dispensing errors or discrepancies are discovered.

Prior to site closure and at appropriate intervals during the study, site CRA will perform study drug accountability and reconciliation. At the end of the study, the Investigator will retain all the original documentation regarding study drug accountability, return, and/or destruction, and copies will be sent to the Biorasi/Sponsor.

All unused and used Study Drug tubes will be returned to the Sponsor or its designee for destruction at the end of the study except for the Retention Samples.

5.10 Prior, Concomitant and Prohibited Therapy

Current medications and any medications taken within the 30 days prior to the start of the study will be recorded as prior/concomitant medications (using their generic name, if known) with the corresponding indication, start and stop dates. The medications to be recorded include prescription and all over-the-counter (OTC) medications and all dietary supplements. All medications taken on a regular basis, including aspirin and acetaminophen, should be recorded prior to commencing the use of the investigational product. Any medications started during the study (including "as needed" medications) will be recorded in the concomitant medication list as soon as the Investigational Site will become aware of the medication being added.

Prohibited Therapies are those medicinal products and treatment methods that are not allowed in the current study within the timeframes specified in the Table 3.

Table 3. List of Prohibited Medication and Treatment Methods

Treatment	Timeframe the Therapy is Prohibited	
Systemic corticosteroid or immunosuppressive drugs		
Treatment of EAWs, including surgical removal (cryosurgery, laser ablation, electrocoagulation, shaving, etc.), over-the-counter (OTC) treatments, Trichloroacetic acid (TCA) or bichloroacetic acid (BCA) solution, etc.	4 weeks prior to the Baseline visit and until the EOS/ET visit	
Any other topical products applied to the treatment area(s)	From the Baseline visit and until the EOS/ET visit	
Antipruritic (anti-itch medication), including antihistamines	within 24 hours of study visits	
Immunomodulators	From the Baseline visit and until the EOS/ET visit	
Immunostimulatory drugs	From the Baseline visit and until the EOS/ET visit	
Interferon	From the Baseline visit and until the EOS/ET visit	
Another Investigational Drug	90 days prior to the Screening visit and until the EOS/ET visit	

If the Investigator becomes aware of a subject having taken a prohibited medication, they will report the incident to the Medical Monitor and Biorasi within 24 hours, and the Medical Monitor and/or Sponsor will provide written approval of the subject's continuation or discontinuation from the study.

Confidential Page 33 of 59

6 STUDY PROCEDURES AND SCHEDULE OF ACTIVITIES

The following sections describe the procedures to be completed during the study. Subjects are to be assessed by the same Investigator or site personnel whenever possible.

6.1 Administrative Procedures

6.1.1 Subject Informed Consent

A signed and dated, study-specific, approved by Institutional Review Board (IRB)/Independent Ethics Committee (IEC) and applicable regulatory authorities Informed Consent Form must be obtained from each subject prior to performing any study related procedures. No study related procedures or activities may be performed until each subject is fully informed and the consent form is signed and dated.

A copy of the signed consent (or a second original) will be given to every participant (or legally authorized representative) and the original will be maintained with the participant's records.

Subjects that require a wash-out of more than 30 days from their initial informed consent/ signing must be re-consented before any further study procedures can begin.

6.1.2 Documentation of Screen Failures

Investigators must account for all subjects who sign informed consent and will maintain an Enrollment log capturing subjects screened and indicating who was enrolled or excluded and the reason why. If the subject is found not to be eligible prior to enrollment, the reason(s) for ineligibility must be documented by the Investigator.

Subject Numbers assigned to subjects who fail Screening will not be re-used.

6.2 Study Procedures and Evaluations

6.2.1 Clinical Evaluations

The following clinical evaluations will be conducted during the study:

6.2.1.1 Subject Demographics

Basic demographic information, including date of birth, sex, ethnicity, and race will be recorded at the Screening visit.

6.2.1.2 Medical history

Medical history will be collected at the Screening visit. Relevant medical history, including any history of HPV infections and EAWs will be documented. Presence of immunodeficiency, or other clinically significant ongoing medical condition or disease will disqualify subject from participation.

Confidential Page 34 of 59

6.2.1.3 Concomitant Medication Recording

All medications (both prescription and nonprescription, and including vitamins, herbals, topicals, inhaled, and intranasal) taken within 30 days prior to the start of the Study Treatment and through the final study visit will be recorded on the appropriate eCRF (using their generic and brand name, if known) with the corresponding indication, start and stop dates. At each study visit, subjects will be asked whether they have started or discontinued any medication since their previous study visit. This includes single use or PRN (pro re nata, as needed) medication use.

Previous treatment of HPV infection with any formulation of Podofilox must be recorded irrespectively of the term it was given. Corresponding condition shall be captured in the subject's Medical History.

6.2.1.4 Vital Signs

Vital signs will be collected at each study visit. Vital signs will include body temperature, pulse rate and blood pressure (systolic and diastolic). Blood pressure and pulse rate will be measured after the subject has been sitting restfully for at least 5 minutes.

Any abnormal characteristics will be evaluated by the Investigator from based on their significance. Abnormal vital signs will be considered AEs if they require therapeutic medical intervention, and/or if the Investigator considers them to be AEs due to the clinical judgement.

6.2.1.5 Physical examination

Physical examination, including height, weight, and evaluation of organs and systems (General Appearance, Heart/Cardiovascular, Lungs, Gastrointestinal, Ears / Nose / Throat, Extremities, and Skin) will be assessed at the Screening, Baseline and EOS/ET visits.

Clinically significant abnormalities other than presence of external anogenital warts will disqualify subject from participation. The following skin abnormalities are also considered disqualifying:

- Internal genital warts
- Mucous membrane warts
- Bowenoid papulosis
- Squamous cell carcinoma
- Active Herpes lesion within any treatment area
- Eczema
- Skin that had not healed following surgical procedure (cryosurgery, laser ablation, or similar).

6.2.1.6 Visual Examination of External Anogenital Warts

Visual examination at the Screening visit aims to confirm the clinical diagnosis of external anogenital warts based on positive identification of perianal warts and/or external genital warts. Two or more distinct external genital warts, and wart area that is equal to or less than 10 cm² are required for participation in the trial (refer to Section 4.1.1).

Histological confirmation should be obtained at the discretion of the PI if there is any doubt of the diagnosis and to rule-out skin lesions of different origin, such as mucous membrane wart, Bowenoid papulosis, Squamous cell carcinoma, or active Herpes lesions.

Confidential Page 35 of 59

The Investigator will record total number of anogenital warts within treatment area(s), indicating:

- (a) total number of external genital warts and
- (b) perianal warts at each study visit.

A cluster of warts is to be counted as a single wart. As far as possible, the same physician will perform the record for the same subject throughout the study.

Visual examination of EAWs will be repeated at each study visit. Total disappearance of all warts within all treated areas will be considered a "treatment success".

6.2.1.7 Assessment of Local Application Site Reactions

Local skin reaction scores for erythema, dryness, burning/stinging, erosion, edema, pain, itching and bleeding will be recorded by the Investigator for every study visit based on their intensity.

Table 4. Skin Reaction Scale

Reaction	Score, 0-3*
erythema	
dryness	
burning/stinging	
erosion	
edema	
pain	
itching	
bleeding	

^{*} Scores are: 0=absent, 1=mild (slight, barely perceptible), 2=moderate (distinct presence), 3=severe (marked, intense)

The Application Site Reaction Assessment must be conducted by qualified investigators listed on the Form FDA 1572 who have been delegated these tasks by the PI. The PI may delegate this task to Physicians, Physician Assistants, or Nurse Practitioners, Registered Nurses (RNs) or Licensed Practical Nurses (LPNs) who have documented training and past experience conducting this assessment.

Application site reactions (erythema, dryness, burning/stinging, erosion, edema, pain, itching, and bleeding) are to be recorded as adverse events of special interest.

All application site reactions must be recorded as adverse events in the source document and eCRFs.

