1.2.3 Safety Profile

In clinical trials with Condylox® Gel 0.5%, the following local adverse reactions were reported during the treatment of anogenital warts:

Table 2. Local adverse reactions reported in Condylox® Gel 0.5% clinical trials

Adverse Reaction	Mild	Moderate	Severe
Inflammation	32.2%	30.4%	9.3%
Burning	37.1%	25.9%	11.5%
Erosion	27.0%	20.8%	8.9%
Pain	23.7%	20.4%	11.5%
Itching	32.2%	16.0%	7.8%
Bleeding	19.2%	3.0%	0.7%

The severity of local adverse reactions was predominantly mild or moderate and did not increase during the treatment period. Severe reactions were most frequent within the first 2 weeks of treatment.

Other local adverse reactions reported included stinging (7%), and erythema (5%); less commonly reported local adverse events included desquamation, scabbing, discoloration, tenderness, dryness, crusting, fissures, soreness, ulceration, swelling/edema, tingling, rash, and blisters. The most common systemic adverse event reported during the clinical studies was headache (7%).¹⁴

Further details are provided in the Investigator's Brochure [IB]¹⁵.

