2.2.2 Secondary Endpoint (Safety Endpoints)

Local application site reactions scores (erythema, dryness, burning/stinging, erosion, edema, pain, itching and bleeding) in each group during the study drug application period.

Other adverse events including serious adverse events throughout the study participation.

Confidential Page 24 of 59

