7.2 Adverse Event Severity

The Investigator will use the following definitions to rate the severity of each AE and SAE:

Mild	The event is transient and easily tolerated by the subject.
Moderate	The event causes the subject discomfort and interrupts the subject's usual activities.
Severe	The event causes considerable interference with the subject's usual activities and may be incapacitating or life-threatening.

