4.2.2 Secondary (Safety) Endpoints

Adverse events will be summarized by frequency, by severity and will be tabulated by body system/organ class.

Confidential

Local application site reactions scores (erythema, dryness, burning/stinging, erosion, edema, pain, itching and bleeding) in each group during the study drug application period will be summarized by type of reaction and by intensity score.

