	from Baseline	Absent	xx (xx.x)	xx (xx.x)	xx (xx.x)	xx (xx.x)
		Present	xx (xx.x)	xx (xx.x)	xx (xx.x)	xx (xx.x)
		Mild	xx (xx.x)	xx (xx.x)	xx (xx.x)	xx (xx.x)
		Moderate	xx (xx.x)	xx (xx.x)	xx (xx.x)	xx (xx.x)
		Severe	xx (xx.x)	xx (xx.x)	xx (xx.x)	xx (xx.x)

Table 14.3.7Summary of Site Reaction by Intensity and Visit, Safety Population

Repeat for Site reactions: dryness, burning/stinging, erosion, edema, pain, itching, and bleeding.

Then Repeat for visit 4, 5, 6 and EOS.

n: number of patients affected. Test Product: Podofilox Topical Gel 0.5% Reference: Condylox® Gel 0.5% Placebo: vehicle that matches the test product

Source: <Dataset>

Program Name: <Pgm name>

Listing: 16.3.7 Date: YYYY-MM-DD Time: HH:MM:SS

Protocol: 16-POD-001 Version 2.0, 15-Jan-2018

Confidential

	Overall Summary o	of Adverse Events, Safe	ety Population	
	Test Product (N=xxx) n (%)	Reference (N=xxx) n (%)	Placebo (N=xxx) n (%)	All Subjects (N=xxx) n (%)
Total number of AEs	XX	XX	XX	XX
Total number of SAEs	XX	XX	XX	XX
Total Number of TEAEs	XX	XX	XX	XX
Total Number of TESAEs	XX	XX	XX	XX
Number of Subjects with:				
At Least One TEAE	xx (xx.x)	xx (xx.x)	xx (xx.x)	xx (xx.x)
At Least One Related TEAE	xx (xx.x)	xx (xx.x)	xx (xx.x)	xx (xx.x)
At Least One Severe TEAE	xx (xx.x)	xx (xx.x)	xx (xx.x)	xx (xx.x)
At Least One TEAE Leading to				
Discontinuation	xx (xx.x)	xx (xx.x)	xx (xx.x)	xx (xx.x)
At Least One TEAE Leading to			× ,	
Death	xx (xx.x)	xx (xx.x)	xx (xx.x)	xx (xx.x)
At Least One TESAE	xx (xx.x)	xx (xx.x)	xx (xx.x)	xx (xx.x)
At Least One Related TESAE	xx (xx.x)	xx (xx.x)	xx (xx.x)	xx (xx.x)
At Least One Severe TESAE	xx (xx.x)	xx (xx.x)	xx (xx.x)	xx (xx.x)
At Least One TESAE Leading to		. ,		
Discontinuation	xx (xx.x)	xx (xx.x)	xx (xx.x)	xx (xx.x)

Table 14 3 8

(S)AE: (Serious) Adverse Event reported from signature of the Informed Consent Form to 30 days following the last study drug application. TE(S)AE: Treatment Emerging (Serious) Adverse Event reported during the treatment period (from the day of the first application of the study drug and up to the last visit). Test Product: Podofilox Topical Gel 0.5% Reference: Condylox® Gel 0.5% Placebo: vehicle that matches the test product

Source: <dataset></dataset>	Listings: 16.3.8.1 – 16.3.8.2 – 16.3.8.3	Snapshot Data DD-MMM-YYYY
Program Name: <pgm name=""></pgm>	Date: YYYY-MM-DD Time: HH:MM:SS	Programmer: < Programmer Initials>

Protocol: 16-POD-001 Version 2.0, 15-Jan-2018

Confidential

Table 14.3.8.1.1

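### The SAP's aggregate adverse event rows pool expected local reactions with other events, so the protocol's other-AE safety endpoint has no summary line of its own

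*Protocol*

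**What the plan says.** Protocol 2.2.2 gives two safety endpoints. One is the scores for eight named local reactions during the application period. The other is "Other adverse events including serious adverse events throughout the study participation". The SAP synopsis repeats both.

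Protocol 6.2.1.7 has each of the eight reactions scored 0 to 3 at study visits. It says that they "are to be recorded as adverse events of special interest" and adds that "All application site reactions must be recorded as adverse events in the source document and eCRFs".

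SAP 4.2.2 words the AE endpoint as "Adverse events will be summarized by frequency, by severity and will be tabulated by body system/organ class". The restriction to other events has gone, and nothing excludes local reactions.

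In the SAP table shells (12.1.1), Table 14.3.8 has total counts, then subjects with any TEAE, "At Least One Related TEAE", "At Least One Severe TEAE", TEAEs leading to discontinuation or death, and the serious-event counterparts. Tables 14.3.8.1.1 to 14.3.8.1.3 have an any-event line followed by system organ class and preferred-term rows; the second and third split these by severity and by causality. Local scores have Table 14.3.7 and serious TEAEs have Table 14.3.8.2. The list of tables contains no special-interest table and no TEAE table without local reactions.

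**The concern.** The protocol separates two safety questions at the endpoint level and then puts the answer to the first into the data for the second. Because the SAP does not separate them again in its aggregate rows, a reader of the overall AE table cannot learn how many subjects in each arm had an AE other than an expected local reaction, or how many had a related or severe one. Local reactions to this drug are very common, so the pooled rows will look much alike in the two active arms even if the arms differ in other events. What is at stake is the summary of a stated safety endpoint. The equivalence and superiority analyses do not use these tables.

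**Working it through.** The documents give no figure on this point, so there is none to reproduce. The check is a reading of the table shells followed by simple arithmetic.

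**1. Is there a line for other AEs?**
- Table 14.3.8: every non-serious row counts all TEAEs, with no local/other split.
- Tables 14.3.8.1.1 to 14.3.8.1.3: the any-event line pools both kinds. A system organ class row may pool them too, depending on coding that the documents do not specify.
- Table 14.3.7: local scores only.
- Table 14.3.8.2: serious events only.

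No aggregate line counts subjects with any, related or severe other AE.

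**2. Can the count be rebuilt from the preferred-term rows?** No. A subject with two different events appears on two rows, so adding rows double-counts. Rebuilding it from the listings needs a rule for which terms are local. The documents give none, and the shells of Listings 16.3.8.1 to 16.3.8.3 show no special-interest column.

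**3. How large is the local component?** Inputs are Protocol 1.2.3 with its Table 2 (reference gel) and SAP 5.3 (177 subjects per active arm).
- Burning: 37.1 + 25.9 + 11.5 = 74.5%. In an arm of 177: 0.745 × 177 ≈ 132 subjects.
- Headache, the commonest systemic event: 7%. In an arm of 177: 0.07 × 177 ≈ 12 subjects.
- Severe burning and severe pain: 11.5% each. In an arm of 177: 0.115 × 177 ≈ 20 subjects for either one.

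**4. How much is a contrast diluted?** Let L be the proportion with a local reaction and x the proportion with an other AE. Under independence, any TEAE = 1 − (1 − L)(1 − x), so a difference in x shrinks by the factor 1 − L. With L = 0.745 in both arms the factor is 0.255.

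| Other AEs, assumed | True difference | Pooled any-TEAE rates | Pooled difference |
|---|---|---|---|
| 7% v 14% | 7 points | 76.3% v 78.1% | about 1.8 |
| 10% v 20% | 10 points | 77.1% v 79.6% | about 2.6 |
| 15% v 30% | 15 points | 78.3% v 82.2% | about 3.8 |

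For example, 1 − 0.255 × 0.93 = 0.763 and 1 − 0.255 × 0.86 = 0.781.

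**5. How sensitive is this?** Burning alone is a lower bound for any local reaction at the Table 2 rates. If the six reaction types in Table 2 were independent, L would be 1 − 0.281 × 0.255 × 0.433 × 0.444 × 0.440 × 0.771 = 99.5%, and all three contrasts would fall below 0.1 point. That is an extreme, since reactions at one site probably occur together. Dilution is also stronger if other AEs cluster in subjects with local reactions, and weaker if they fall mainly in subjects without.

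**6. What is not diluted?** A 7% versus 14% contrast in headache would show as 7 points on its own preferred-term row. Serious events are read from Table 14.3.8.2.

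**7. The two severity scales.** On the 0 to 3 score, moderate means that the reaction is distinctly present at the visit. For an AE, Protocol 7.2 defines moderate as "The event causes the subject discomfort and interrupts" usual activities. Table 14.3.7 reports the score by visit, while the AE summaries take the greatest severity per preferred term (SAP 10.1.1). The same reaction can therefore be graded differently in the two places without either entry being wrong.

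**The case against.** The strongest reply is that the endpoint is already reported. Each non-local preferred term has its own row by arm, with severity and causality; serious events, which the endpoint expressly includes, have their own table; and local reactions have Table 14.3.7. The secondary objective (Protocol 2.1.2, SAP 4.1) refers to the frequency and severity of adverse events without the restriction to other events, so a pooled table answers it. Safety reporting is descriptive, so no planned test is weakened. And 7% is the rate of one event, not of any other AE.

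Most of this stands. It limits the point to the aggregate rows, supports keeping the pooled line, and makes the rates in the dilution table illustrative. It does not supply the missing count, because overlapping preferred-term rows do not add up to it.

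A reader might also infer that AE severity for local reactions should be taken from the 0 to 3 score so that the tables agree. The documents do not support this. Drug is applied on the first three days of each cycle, and the visit falls on day 7, at the end of the four rest days. The diary captures reactions between visits (Protocol 6.2.3). A reaction that was severe on day 2 and gone by day 7 would score 0, and the substitution would erase it. Protocol 7.2 also has the investigator rate every AE by its effect on the subject, which is a different measure.

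**Conclusion.** The point holds for the aggregate rows. The protocol states an other-AE endpoint, and the SAP gives no line for subjects with any, related or severe other AE. At the reference-gel rates, at least about three quarters of an active arm would enter the any-TEAE row through burning alone, and a contrast in other AEs would keep roughly a quarter of its size there.

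This assumes that Table 2 rates apply to both active arms, that local and other AEs are independent, and that the illustrative rates of 7% to 30% are plausible. The documents give neither a vehicle rate nor a rate for any other AE.

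Two stronger readings are not supported. One is that the whole endpoint is swamped or unmeasured; the preferred-term rows and the serious-event table show otherwise. The other is that the headline rates will sit near the ceiling. The documented floor gives about 76% to 82% in the scenarios above, and a rate near 100% needs independence between reaction types, which nothing in the documents supports. A figure of 11.5% severe for burning or pain is far from a ceiling.

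This is a reporting gap worth closing because closing it is cheap. It has no bearing on the primary analysis, the sample size or what is collected.

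**What to change.** Before database lock:

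1. In SAP 4.2.2 and 10.1.1, define an other AE as any AE that is not one of the eight application site reactions named in Protocol 6.2.1.7 as events of special interest. State how coded terms map to the eight, and note that an application-site event of another kind then counts as other.
2. In Table 14.3.8 and in the total rows of Tables 14.3.8.1.1 to 14.3.8.1.3, report local application site reactions and other AEs separately, beside the pooled line. Read the second endpoint of Protocol 2.2.2 from the other-AE lines.
3. Leave AE severity as the investigator rated it. Footnote Table 14.3.7 and the AE severity tables with the scale that each one uses.

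The cost is slightly longer tables in four places and a derived flag. The protocol gives the special-interest label, but the SAP and its listing shells do not carry it, so the flag has to be defined and programmed. SAP 7.4 lets layout changes pass without a revision; a new derived variable goes beyond layout and should be written into the SAP. No new data, visits or subjects are needed.
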